Insomnia Severity Index (ISI). The ISI is a seven-item global index of self-reported insomnia symptom severity. It is valid, reliable, sensitive to changes in insomnia treatment (Bastien, Vallieres, & Morin, 2001; Morin, Belleville, Belanger, & Ivers, 2011) and validated for online use (Thorndike et al., 2011). Seyffert and colleagues (2016) categorized insomnia severity by scores as follows: 0-7 = no clinically significant insomnia, 8-14 = subthreshold insomnia, 15-21 = moderate insomnia, and 22-28 = severe insomnia. Changes in the ISI over time will be a primary outcome measure. The ISI is collected within the SHUTi intervention program at the beginning of each core, but participants in both Phase I and Phase II will also complete a paper version of the ISI during the pre-, mid-point, and post-test assessments.

Daily sleep and symptom diaries. Prospectively collected sleep diaries are a proven method for assessing insomnia and track treatment effects (Carney, et al., 2012; Buysse, Ancoli-Israel, Edinger, Lichstein, & Morin, 2006) and have been used for other sleep studies among patients on 1SE (inpatient and outpatient). Participants will be asked to complete at least five out of every seven days of daily sleep and symptom diaries. These diaries will include sleep/wake times, time in bed, sleep onset latency, number and duration of awakenings, sleep quality, naps, alcohol consumption, any over-the-counter or prescription medications used to help with sleep (participants will be instructed to include any marijuana use in this section), and open-ended comments. For the experimental group, diaries will be used to assess adherence to their “sleep window,” based on actual time in bed as a proportion of prescribed time in bed. We will cross-validate diary-reported sleep duration with actigraphy data when possible. Secondary outcome measures captured in the diaries will include a categorical measure of relapse (i.e. whether the participant reports any drinking post-discharge) as well as quantity and frequency of drinking, which will be calculated in the case of relapse, as well as all other diary variables.

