2.5 Inclusion and Exclusion Criteria

2.5.1 Participants will be eligible for this study if they:

- Are 18 – 65 years old
- A score of 10 or higher on the Insomnia Severity Index*
- Are admitted as a treatment-seeking inpatient on 1SE under protocol 14-AA-0181 (signing both the clinical and research consent)
- Have been inpatient for at least 14 days prior to consent/screening
- Can speak, understand, and write in English
- Are able to comply with study requirements (including ability to access the Internet at least 2x per week)

2.5.2 Participants will be ineligible for this study if they:

- Are pregnant
- Are a prisoner
- Report a physician diagnosis of moderate to severe obstructive sleep apnea (OSA) OR test positive for moderate to severe OSA as documented with an Apnea Hypopnea Index of 15 events/hour based on WatchPAT testing results
- Have irregular sleep schedules that prevent the ability to follow treatment recommendations (i.e. usual bedtimes outside of 8:00 pm to 2:00 am or arising times outside of 4:00 am to 10:00 am)
- Meet SCID-5/DSM-5 criteria for opioid use disorder in the past year
- Meet SCID-5/DSM-5 criteria for severe cocaine use disorder and/or severe cannabis use disorder in the past year
- Meet diagnostic criteria for an unstable or serious psychiatric condition (schizophrenia, bipolar, major depressive disorder not currently in remission) - based on diagnosis from the SCID for DSM-5
- Are participating in any experimental pharmacological intervention study
- Presence of unstable or serious medical/neurologic illness at PI and MAI discretion

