Cocaine is a stimulant that can disrupt sleep and sleep architecture in both humans and animals (Angarita, Emadi, Hodges, & Morgan, 2016; Cortes et al., 2016; Irwin, Bjurstrom, & Olmstead, 2016). Increased arousal is the most common effect of cocaine use with regards to sleep and animal models showed that the level of arousal is dose dependent (Chakravorty, Vandrey, He, & Stein, 2018; Cortes et al., 2016). Individuals who are diagnosed with cocaine use disorder (CoUD) have an underlying sleep disturbance that may persist even after abstinence for several weeks, although recent evidence suggests that improving sleep may increase the likelihood of sustained abstinence from cocaine (Angarita et al., 2016; Hodges, Pittman, & Morgan, 2017; Winhusen, Theobald, & Lewis, 2019). CoUD as well as other substance use disorders are commonly comorbid with AUD (Chakravorty et al., 2018). For this study, we will only exclude participants who meet the DSM-5 criteria for severe CoUD. During analysis, we will attempt to control for any comorbid substance use disorders.

Opioids are associated with a more complex picture of sleep disorders that includes insomnia, obstructive sleep apnea, and complex sleep apnea (Hassamal, Miotto, Wang, & Saxon, 2016). Patients who are diagnosed with opioid use disorder are usually treated with oral naltrexone. "Oral naltrexone is capable of inducing fatigue, nausea, sleepiness, restlessness, and dysphoria in nonopiate users during the first few hours acutely post-ingestion" (Mysels, Cheng, Nunes, & Sullivan, 2011, p.22). Insomnia also transiently worsened with naltrexone treatment, but it is purported to be associated with subacute opiate withdrawal (Mysels et al., 2011). Thus, we are excluding participants who meet the SCID-5/DSM-5 criteria for opioid use disorder regardless of severity.

A previous study on predictors of dropout in a CBT-I program indicated a drop-out rate of around 34%. Based on potential dropout of those individuals who are eligible and are randomized in Phase II (conservative estimate: 40%), and a target of 20 individuals per group, we have adjusted our accrual ceiling to 67 (plus 12 for Phase I). We will submit an amendment to adjust this number if we discover the prevalence and severity of OSA in the population is higher than our estimate based on results from the WatchPAT screening.

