Any experimental pharmacological agent may affect the data collected for this study and its effect on sleep will be largely unknown. As a result, our research team decided on excluding participants that are enrolled in any experimental pharmacological study.

PI Name: [name]

Version Date: 12/07/2020

Protocol Number: 18-CC-0079

Study measures have only been validated in English.

Additional note: after enrollment in the study, the management of sedatives/hypnotics for individuals who have been prescribed either will be done by a clinician who is blind to the treatment condition.

Protocol Number: 18-CC-0079

3 Statistical analysis:

Qualitative analysis (Phase I participants only). Each audio-recorded interview will be transcribed verbatim. A codebook will be developed based on themes from the interviews. Each code will be accompanied by an operational definition that will allow for clarity and consistency in the coding process. Evidence of each code or theme will be assessed using quotes from the interviews. A team of coders will independently review all transcripts. Discordant coding will be discussed until consensus among the coding team is achieved. Once the iterative process of consensus building is complete, an intramural expert in qualitative methodology will validate the final themes and coding. After data are coded, NVivo will be utilized for further qualitative analysis and data management.

Quantitative analyses (Phase II only). The first step in quantitative data analysis will be running baseline "diagnostics" to check for outliers and normal distribution of all continuous variables. If the assumptions of normality are not violated, we will proceed with parametric testing. If the assumptions of normality are violated, non-parametric tests will be utilized. For quantitative analyses, statistical significance will be considered at $p < 0.05$.

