Phase II: 60 participants - the total sample size for phase II of this study will test the primary hypotheses associated with the analysis plan. With insomnia severity as the primary outcome, we will use a two-sided alternative hypothesis that the rate of change will be different between the intervention group and the control group. Assuming a correlation of 0.6 between the two time points, an alpha level of 0.05, a power level of 0.8, and an estimated attrition rate of 40 percent, we will be able to detect an effect size of 0.84 with 60 participants (Fitzmaurice, Laird, & Ware, 2012). Permuted block randomization with block size of four will be used to equally assign participants in each group. The statistician, who will not have any contact with participants, will prepare the randomization sequences and give out the allocation assignment after each participant is consented.

Mixed model for repeated measure with group, time, and the interaction of group by time will be used to test the changes of insomnia severity in two groups. Mixed model for repeated measures will also be used to test the secondary objectives with potential covariates in the model. Demographic, psychiatric, and/or drinking-related factors significantly related to the outcomes listed in the secondary objectives will be entered in the model. Aikake information criterion and the Bayesian information criterion will be used to select best-fitting models. A potential dosing effect analysis including the number of cores completed as a covariate will be conducted for the treatment group only. With the linear mixed model approach, all available data points will be included in the analyses. Under missing completely at random and missing at random assumptions, linear mixed model with restricted maximum likelihood estimation can produce unbiased estimators (Salim, Mackinnon et al. 2008).

Investigator Conflicts: NIH guidelines on conflict of interest have been distributed to all investigators. NIH guidelines on conflict of interest have been distributed to all investigators.

Technology Transfer: No technology transfer agreement is in place for this protocol.

4 Rationale for subject selection

This study will be open to both males and females of all racial and ethnic groups, without targeting any specific group. We anticipate the target enrollment of participants to reflect the racial/ethnic distribution of residents in the greater Washington DC metropolitan area.

5 Recruitment plan

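### Optional efficiency gain: adjusting the planned ISI mixed model for pre-randomisation ISI adds about 5 points of power if baseline and post-test SDs are equal, but about 1 point or less if the entry cutoff narrows the baseline SD to 0.7-0.8 of post-test

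*Combined protocol and SAP*

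**What the plan says.** In Section 3, the Phase II sample-size paragraph frames the hypothesis as two-sided, namely that "the rate of change will be different between the intervention group and the control group". The inputs are given as "Assuming a correlation of 0.6 between the two time points, an alpha level of 0.05, a power level of 0.8", with 40% attrition and a detectable effect of 0.84 from 60 participants. The model follows: "Mixed model for repeated measure with group, time, and the interaction of group by time will be used". Covariates are mentioned only for the secondary objectives, and baseline ISI is not named among them. On missing data the plan says "With the linear mixed model approach, all available data points will be included in the analyses".

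Section 2.4 has ISI collected three times; participants "will also complete a paper version of the ISI during the pre-, mid-point, and post-test assessments". Pre-test ISI is therefore naturally read as one of the repeated responses, with its own mean in each arm. Section 2.5.1 sets the entry rule: "A score of 10 or higher on the Insomnia Severity Index". Section 2.3 uses a screening ISI to apply it.

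**The concern.** Randomisation makes the expected baseline ISI the same in both arms. A model that lets each arm have its own baseline mean does not use that fact. Its pre-to-post contrast subtracts the observed baseline difference with a weight of one. The most efficient weight is the regression slope of post-test on baseline, which is 0.6 when the correlation is 0.6 and the SDs are equal. Over-subtracting adds noise. With 60 people and 40% attrition, about 36 complete, so precision from a measurement already being collected is worth having.

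What is at stake is power and the width of the confidence interval. The validity of the test is not in question.

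**Working it through.** **Inputs.** From Section 3: two-sided alpha 0.05, power 0.80, correlation ρ = 0.6, effect 0.84 (in post-test SD units), 60 randomised 1:1, 40% attrition. That gives 30 per arm with 30 × 0.6 = 18 completing. Assumption: k, the ratio of baseline SD to post-test SD, is not given in the documents and is varied below. Power is Φ(0.84/√V − 1.96), and the detectable effect is (1.96 + 0.84)√V, where this second 0.84 is the normal quantile for 80% power.

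**1. The plan's own figure.** The change-score variance factor with equal SDs is 2(1 − 0.6) = 0.80. With 18 per arm, V = 2 × 0.80/18 = 0.0889. The detectable effect is 0.835 and power at 0.84 is 80.4%. The required 18 per arm, inflated for attrition, is 36/0.6 = 60. The plan's 0.84 with 60 is therefore an unadjusted change contrast in completers.

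**2. Completers, adjusted for baseline.** The variance factor is 1 − 0.6² = 0.64. V = 2 × 0.64/18 = 0.0711, detectable effect 0.747, power 88.3%. With t critical values, and the cost of estimating the slope included, power goes from 78.1% to 85.3% and the detectable effect from 0.860 to 0.782.

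**3. All available data, as the plan states.** Suppose the 12 dropouts per arm contribute baseline only. The two contrasts have variances

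- free baseline means: V = 2[(1 − ρ²)/18 + (ρ − k)²/30]
- common baseline mean: V = 2(1 − ρ²)/18

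With ρ = 0.6 and k = 1, the first is 2[0.64/18 + 0.16/30] = 0.0818 (power 83.6%) and the second is 0.0711 (88.3%). Adding mid-point ISI under compound symmetry gives:

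| When the 12 dropouts per arm leave | V, free | V, common | Power, free | Power, common |
|---|---|---|---|---|
| all before mid-point | 0.0818 | 0.0711 | 83.6% | 88.3% |
| 6 before, 6 after | 0.0793 | 0.0686 | 84.7% | 89.4% |
| all after mid-point | 0.0778 | 0.0671 | 85.4% | 90.0% |

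The gain is about 4.7 points in each row. Small-sample simulation with an unstructured covariance gives lower levels and a similar gain: 81.0-82.7% to 85.3-87.4%.

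**4. Sensitivity to the SD ratio (ρ = 0.6, 6 and 6 dropout).**

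| k | Free | Common | Gain (points) |
|---|---|---|---|
| 1.0 | 84.7% | 89.4% | 4.7 |
| 0.9 | 86.8% | 89.4% | 2.6 |
| 0.8 | 88.2% | 89.4% | 1.2 |
| 0.7 | 89.1% | 89.4% | 0.3 |

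The formula in step 3 shows why: the penalty is (ρ − k)², which vanishes when k equals ρ.

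**5. Sensitivity to the correlation (k = 1, same dropout).** 0.4: 69.6% to 79.3%. 0.5: 76.7% to 83.9%. 0.7: 92.8% to 95.0%. 0.8: 98.6% to 99.1%. The gain runs from about 10 points to under 1.

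**6. Cost when baseline adds nothing over the change score.** At ρ = 0.7 and k = 0.7, t-based power moves from 92.9% to 92.1%, a loss of under 1 point from the extra degree of freedom.

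**The case against.** The strongest reply is that nothing here is an error. A group-by-time mixed model using all available data is a standard choice for a pilot trial, and its sample size reproduces. That stands, and it is why this is offered as an optional improvement.

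Second, equal SDs are an assumption. Entry at ISI 10 or higher cuts the lower tail at baseline but not at post-test. As an illustration under assumed values, take a normal ISI with mean 14 and SD 6. The cut lies 4/6 = 0.667 SD below the mean, and the truncated SD is √(1 − 0.667 × 0.427 − 0.427²) = 0.73 of the full SD, where 0.427 is the normal density over the retained proportion. At k of 0.7-0.8 the gain is about 1 point or less. This also stands. It is softened only if the 0.6 came from an unselected sample: truncation would then lower the correlation too, and the gain would lie between that and 5 points.

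Third, adjustment needs a baseline taken before allocation. The Table of Measures in Section 2.4 places pre-test before program start, which is not the same as before randomisation. This stands and shapes the fix.

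Fourth, the plan does not say whether the interaction is a single contrast or a joint test over visits. A reader might infer that moving to one post-test contrast is always an improvement. It is not. If the effect is already full at mid-point and half or all dropouts supply mid-point data, an unadjusted joint two-degree-of-freedom test has 92.8-95.6% power, against 89.4-90.0% for the adjusted single contrast. If the mid-point effect is half the final one, the joint test has about 77-79%. The gain claimed here is only for adjustment within the same contrast.

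**Conclusion.** The point holds as an optional efficiency gain. At the plan's effect of 0.84 and correlation of 0.6, using all available data, baseline adjustment of the pre-to-post contrast adds about 5 points of power with equal SDs, about 3 at a ratio of 0.9, about 1 at 0.8 and near 0 at 0.7. This rests on 30 randomised and 18 completing per arm, compound symmetry and a one-degree-of-freedom test. With equal SDs but other correlations, the range is about 10 points at 0.4 to under 1 at 0.8.

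Some stronger readings are not supported:

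- **The trial is underpowered or the 0.84 is wrong.** The figure reproduces, and the planned all-data test does slightly better than the completer calculation behind it.
- **The gain is 80% to 88%.** That applies to completers only, whereas the plan analyses all available data.
- **The gain is 10 points.** That needs a correlation of 0.4, which is not the plan's value.

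The ordering of sleep efficiency as a second primary outcome, the switch to non-parametric tests after a normality check, and the ISI entries in the Table of Measures are separate matters and carry no weight here.

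**What to change.** In the Phase II paragraphs of Section 3, keep the mixed model and its use of all available data, and add one of two things: baseline ISI as a covariate, or a common baseline mean for the two arms. The baseline should be the pre-test ISI if it is taken before allocation; otherwise use the screening ISI of Section 2.3. State which.

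With a common baseline mean, the between-arm difference at post-test equals the between-arm difference in pre-to-post change, so the stated hypothesis is kept. State the detectable effect for this adjusted contrast: about 0.75 with 18 completers per arm at correlation 0.6, or about 0.78 with t critical values, both assuming equal SDs. Say that the figure depends on the SD ratio.

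If a joint test over all visits is intended, keep it; whether to replace it is a separate decision.

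The cost is a wording change and at most one degree of freedom, under 1 point of power in the case where adjustment brings nothing. No extra data, visits or participants are needed.

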5.1 Informed Consent Process and Procedures

All eligible participants will receive a verbal explanation in terms suited to their comprehension of the purposes, procedures and potential risks of the study and of their rights as research participants. Participants will have the opportunity to carefully review the written consent form and ask questions regarding this study prior to signing. Qualified staff (PI or a designee) will review and discuss the consent form with the volunteer at the study visit, as well as answer any questions that volunteers might have concerning the study procedures and/or other aspects of the consent form. The original signed consent form will be placed in the medical record and a copy will be given to the individual. The participant will

Protocol Number: 18-CC-0079

be informed that a patient rights representative is available to volunteers. After providing written informed consent, screening and all research procedures will be completed.

5.2 Rationale for involvement of vulnerable populations

Not applicable.

5.3 Justification for exclusion of vulnerable populations

Vulnerable populations (including individuals who are pregnant, cognitively impaired, children, and prisoners) will not be enrolled in this study as they are ineligible for admission under the screening and assessment protocol (14-AA-0181).

6 Evaluation of Risks/Discomforts and Benefits ratio:

- a. **Benefits:** This study will provide pilot data on the feasibility, acceptability, and efficacy of an internet-based CBT-I program undergoing inpatient treatment AUD. The program may represent an efficacious non-pharmacologic intervention for insomnia in this population, potentially decreasing medication intervention. It is possible that there may be no direct benefit to the participant. However, based on prior literature, we anticipate alleviation or decrease in insomnia in some study participants.
- b. **Risks:** It is possible that answering some of the questionnaires may cause discomfort to participants. Participants may feel uncomfortable wearing the WatchPAT device or the actiwatch device to sleep. Participants may potentially experience a rash and/or pruritus in wearing the WatchPAT or actiwatch. During WatchPAT testing, participants might also experience slight pressure around their finger that is being used for the test. After WatchPAT testing, participants might notice proximal nail fold redness and a few may experience proximal nail fold blister on the finger that is being tested. These side effects will usually resolve within 24-48 hours after the test. Participants will be instructed to report any untoward side effects from WatchPAT testing to the 1SE inpatient unit's clinical staff and to the research team. 1SE clinical staff will monitor the progression of these side effects and treat as necessary. Participants will also be made aware that they can always stop the WatchPAT testing at any time for any reason. Participants in Phase I and those assigned to the SHUTi condition in Phase II may experience daytime sleepiness (and potentially impaired daytime functioning) during the sleep restriction part of the program, particularly if they are taking medications with side effects of drowsiness during the study period.
- c. **Alternative treatments and procedures:** The alternative to participating in this study is not to participate and obtain treatment as usual.
- d. **Procedures for protecting/minimizing risk:** Every effort will be made to address and minimize participant discomfort including scheduling a repeat session or postponing study procedures if a participant becomes uncomfortable. Confidentiality and information technology standards are in place at the intramural programs of the NIH campus to protect electronic repositories of patient data. We selected a minimally-

Protocol Number: 18-CC-0079

invasive diagnostic tool to assess for OSA, requiring only one night of sleeping with the device. It is reasonably expected that these safeguards will protect participants' medical and personal health information, ensuring their privacy. Participants exhibiting excessive sleepiness will be counseled to avoid activities (e.g. drowsy driving and/or using the stove) that will jeopardize their safety and the safety of others.

- e. **Provisions for ensuring that necessary medical or professional intervention is available in the case of adverse events to the subjects:** The MAI will be made aware of any adverse events to participants directly related to this protocol.

6.1 Protection of Participants' Privacy and Confidentiality

Participants will complete surveys and interviews behind closed doors for privacy. Data will be de-identified where possible through the use of non-identifiable codes. Any personally-identifiable information that participants mention during the interview (specifically their names) will be removed from transcripts and excluded from all data sets and any publications. The key to the code will be kept securely and separate from data and samples. Participant information will be maintained in secure databases and computers in locked files within a locked office. Paper records will be maintained in locked files and a locked office. Access to samples and data will be limited to authorized study personnel. We will be provided with a Certificate of Confidentiality in order to legally refuse to disclose information that may identify participants in any federal, state, or local civil, criminal, administrative, legislative, or other proceedings, for example, if there is a court subpoena. The researchers will use the Certificate to resist any demands for information that would identify you, except in certain circumstances which are clearly outlined in the consent forms.

